### 2.3 Secondary Objectives:

- To determine the reduction of pleural opacity (in percentage) on chest radiograph from day 1 (randomization) to day 7
- To determine the change on inflammatory markers (WBC/CRP) from day 1 (randomization) to day 7
- To determine the outcome :
  - Length of hospital stay (in days) after randomization for each group
  - The need of surgical intervention in 30 days
  - Adverse effects following t-PA/DNase and pleural irrigation
  - Mortality rate at 30 days

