## 2.4 Study Hypothesis

1. Subjects in the IPFT has more volume of pleural fluid drainage compared with pleural irrigation group
2. Subjects in the IPFT has greater reduction of inflammatory parameters compared with pleural irrigation group
3. Subjects in the IPFT has shorter length of hospital stay compared with pleural irrigation group
4. Subjects in the IPFT has less surgical referral rate compared pleural irrigation group
5. There is no difference of mortality rate between both groups

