During any point of treatment subjects will be allowed to cross-over and analysis will be done as per intention to treat. Subjects in the pleural irrigation group may be switched to IPFT group if there is poor response to treatment (poor drainage of effusion), or adverse effects of irrigation as per clinician's judgement. On the contrary, subjects in the IPFT group may be switched to pleural irrigation group if patient developed any adverse effects of IPFT (e.g hemothorax, haemoptysis). Those who failed both treatment will be referred for surgical intervention

Monitoring Parameters :

a. Pleural irrigation group

Parameter	Day0	Day1	Day2	Day3	Day7	Day30
Investigations						

 
• Full blood count (FBC)               
 
○ WBC
 
○ Hemoglobin
 
 
 
	√	√	√	√	√	
• C- reactive protein (CRP)	√				√	
• Chest X-ray	√				√	
• Ultrasound Thorax	√	√	√	√		
Adverse effects						
• Chest pain required escalation of analgesics		√	√	√		
• Gastrointestinal bleed		√	√	√		
• Bleeding from chest drain site		√	√	√		
• Intrapleural hemorrhage		√	√	√		
• Hemoptysis		√	√	√		
• Clinical deterioration – hypotension, dyspnea		√	√	√		
• Hb drop >10% required transfusion blood		√	√	√		
• Death related to intrapleural saline irrigation		√	√	√		

Others Outcome						
• Mortality						
• Surgical intervention						

b. IPFT group

Net Volume of pleural fluid drained (ml) post pleural irrigation	Baseline	Day 1	Day 2	Day 3
	√	√	√	√
Cumulative pleural fluid drained post pleural irrigation				√

b. Intrapleural fibrinolytic group

Parameter	Day0	Day1	Day2	Day3	Day7	Day30
Investigations						
• Full blood count (FBC) 
 
○ WBC
 
○ Hemoglobin
 
	√	√	√	√	√	
• C- reactive protein (CRP)	√				√	

• Chest X-ray	√				√	
• Ultrasound Thorax	√	√	√	√		
Adverse effects						
• Chest pain required escalation of analgesics		√	√	√		
• Gastrointestinal bleed		√	√	√		
• Bleeding from chest drain site		√	√	√		
• Intrapleural hemorrhage		√	√	√		
• Hemoptysis		√	√	√		
• Clinical deterioration – hypotension, dyspnea		√	√	√		
• Hb drop >10% required transfusion blood		√	√	√		
• Death related to intrapleural therapy		√	√	√		
Others Outcome						
• Mortality						
• Surgical intervention						

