### 3.7 Study protocol /flow chart

### 3.7 Statistical Analysis

Statistical analysis will be performed using the available SPSS software version 19. All numerical data will be subjected to normality testing using Shapiro-Wilk test. All normally distributed data will be expressed as mean  $\pm$  standard deviation (SD) whereas non-normally distributed data were expressed as median (IQR). For normally distributed data, parametric test with Student's t-test will be used. For non-normally distributed data, the Mann-Whitney test will be used or equivalent nonparametric tests. Within groups, the Wilcoxon rank sum test will be used. For qualitative data, Chi-Square test and Fisher's Exact test will be used. The significant p-value will be taken as  $<0.05$  or in the case of multiple comparisons it will be adjusted with a Bonferonni correction.

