**Outcome Monitoring:**

Parameter	Day0	Day1	Day2	Day3	Day7	Day30
Investigations						

 
• Full blood count (FBC)               
 
○ WBC
 
○ Hemoglobin
 
 
 
						
• C- reactive protein (CRP)						
• Chest X-ray						
• Ultrasound Thorax						
Adverse effects						
• Chest pain required escalation of analgesics						
• Gastrointestinal bleed						
• Bleeding from chest drain site						

• Intrapleural hemorrhage					
• Hemoptysis					
• Clinical deterioration – hypotension, dyspnea					
• Hb drop >10% required transfusion blood					
• Death related to intrapleural therapy					
Others Outcome					
• Mortality					
• Surgical intervention					

Net Volume of pleural fluid drained (ml) post pleural irrigation	Baseline	Day 1	Day 2	Day 3
Cumulative pleural fluid drained post pleural irrigation				

Other Outcome Measures	
Duration of hospital stay from 1 st dose of intrapleural t-PA/Dnase or 1 st pleural irrigation	Days
Requirement of surgical intervention within 30days from 1 st dose t-PA/DNase or 1 st pleural irrigation (normal saline 0.9%)	Yes / No  If yes, Decortication  Pneumonectomy  Lobectomy 
Outcome upon discharge	Alive  Death 
Readmission within 30 days from discharge for similar complaint (recurrent parapneumonic effusion/empyema)	Yes / No

Complete resolution on radiologically (chest x-ray) on clinic appointment	Yes / No
Mortality within 30 days (from 1 st dose intraplural t-PA/Dnase or normal saline 0.9%) & cause	

Treatment outcome	Successful 
	Failure 

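### Length of stay has no rule for in-hospital death, so taken as written an early death scores as a short, favourable stay

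*Combined protocol and SAP*

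**What the plan says.** Section 2.3 names "Length of hospital stay (in days) after randomization for each group" among the secondary objectives. Section 2.4 gives the direction of benefit: "Subjects in the IPFT has shorter length of hospital stay compared with pleural irrigation group". The data collection sheet (Outcome Monitoring) has the field "Duration of hospital stay from 1", which goes on to name the first t-PA/DNase dose or first irrigation as the start. That differs from the randomization start in section 2.3.

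Section 3.7 (Statistical Analysis) uses Student's t-test for normally distributed data; otherwise, "For non-normally distributed data, the Mann-Whitney test will be used or equivalent nonparametric tests". It mentions no rule for death, such as ranking, censoring or a competing event.

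Two other secondary objectives are measured at day 7: "To determine the reduction of pleural opacity (in percentage) on chest radiograph from day 1 (randomization) to day 7" and "To determine the change on inflammatory markers (WBC/CRP) from day 1 (randomization) to day 7". In section 3.6, patients who fail both treatments are referred for surgery, with no day given. The analysis principle is stated beside the crossover rule: "During any point of treatment subjects will be allowed to cross-over and analysis will be done as per intention to treat". It does not say what value a patient has after death or surgery.

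Death and surgery are recorded. Mortality and surgical intervention at 30 days are outcomes in section 2.3, the operational definition of treatment failure in section 3.6 includes both surgery and death before discharge, and the data sheet has "Outcome upon discharge" (alive or dead).

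**The concern.** A stay ends with discharge alive or with death. A plain count of days treats the two alike, so a patient who dies on day 3 scores better than a survivor who goes home on day 14. If one arm has more early deaths, that arm's stay looks shorter even when survivors in both arms stay equally long, and the analysis reports the excess deaths as a benefit.

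The alternative of leaving deaths out compares survivors only, which is a different question. The plan does not choose between these, and the trial is open-label, so the choice should be fixed before outcomes are seen.

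The day-7 measures have a related gap. A patient who dies before day 7 has no day-7 value, and a film taken after surgery reflects the operation as well as the allocated treatment.

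**Working it through.** **Plan's own figure.** The plan gives none for length of stay. The only design figure is 39 per arm (section 3.3). It reproduces from that section's printed inputs (0.15 v 0.32, power 0.8, two-sided Type I error 0.5 as printed, continuity correction) and serves here only as the number of patients. The printed error rate is a separate matter.

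**Assumptions, none from the documents.**
- Survivors' stay is lognormal with median 14 days and log-SD 0.5, identical in both arms.
- Time to death is lognormal with the same log-SD and median day 5, or day 10 as a variant.
- Mortality is m_A in the worse arm and m_B in the other. The documents give no per-arm rate. The 20–35% in Chapter 1 is an upper range for immunocompromised patients.

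**Shift in the mean.** A lognormal mean is the median × exp(0.5²/2) = median × 1.133. Survivors average 14 × 1.133 = 15.86 days and deaths 5 × 1.133 = 5.67 days. The difference between arms is (m_A − m_B) × (15.86 − 5.67):
- 20% v 10%: 0.10 × 10.2 = 1.0 day shorter in the worse arm
- 30% v 10%: 0.20 × 10.2 = 2.0 days shorter

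**Effect on Mann-Whitney.** Let q be the chance that a death comes earlier than a survivor's discharge: q = Φ(ln(14/5) / (0.5√2)) = Φ(1.456) = 0.927. For median day 10, q = Φ(ln(14/10) / (0.5√2)) = Φ(0.476) = 0.683.

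The chance that a random patient in arm A has a shorter stay than one in arm B is 0.5 + (m_A − m_B)(q − 0.5). With equal mortality this is 0.5 whatever q is, so there is no bias.

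The null standard error is √(79 / (12 × 39 × 39)) = 0.0658. The chance of a significant result for the worse arm is about 1 − Φ(1.96 − shift/0.0658).

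| Mortality | Deaths at median day | Shift | Shift/0.0658 | Worse arm declared shorter |
|---|---|---|---|---|
| 10% v 10% | either | 0 | 0 | 2.5% |
| 15% v 10% | 5 | 0.05 × 0.427 = 0.021 | 0.325 | 5.1% |
| 20% v 10% | 5 | 0.10 × 0.427 = 0.043 | 0.65 | 9.5% |
| 30% v 10% | 5 | 0.20 × 0.427 = 0.085 | 1.30 | 25% |
| 20% v 10% | 10 | 0.10 × 0.183 = 0.018 | 0.28 | 4.6% |
| 30% v 10% | 10 | 0.20 × 0.183 = 0.037 | 0.56 | 8.0% |

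Repeated simulation at 39 per arm agrees: 4–5%, 9–10% and 24–25% for the three day-5 rows with unequal mortality, and about 5% and 8% for the day-10 rows. If deaths occur at the same median as discharge (day 14), q is 0.5 and the bias disappears.

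**With deaths ranked worst.** q becomes 0, so the shift is −0.5 × (m_A − m_B): −0.05 at 20% v 10% and −0.10 at 30% v 10%. Divided by 0.0658 these are −0.76 and −1.52.
- False finding of a shorter stay in the worse arm: Φ(−1.96 − 0.76) = 0.3% and Φ(−1.96 − 1.52) = 0.03%
- Worse arm declared worse: 1 − Φ(1.96 − 0.76) = 11.5% and 1 − Φ(1.96 − 1.52) = 33%; simulation gives about 11% and 32–36%

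**The case against.** **The plan is silent, not wrong.** A reader might infer that the plan states that deaths count as short stays. It does not. That is only what results from applying the listed tests to a plain count of days. This stands, and so the point is a missing rule with a predictable consequence. The flow-chart figure is not shown, so a rule there cannot be excluded.

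**The size is assumed.** It needs both unequal mortality and early deaths. Hypothesis 5 expects no mortality difference, and a small imbalance does little: 12% v 10% gives 3.3% in simulation. This also stands. A reader might infer that hypothesis 3 is likely to be confirmed through deaths on IPFT; the documents give no reason to expect more deaths in either arm.

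**Bonferroni.** Section 3.7 adjusts for multiple comparisons. If that covers the five hypotheses (two-sided 0.01, an assumption), the rates at 20% v 10% and 30% v 10% fall to about 2.8% and 9.1%, against 0.5% by chance. The bias shrinks in absolute terms but remains.

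**Harm is visible elsewhere.** Deaths and surgery are reported separately, and the failure definition counts both. This helps an attentive reader, but 39 per arm is weak protection. Summing the binomial probabilities of all tables with Fisher p < 0.05 gives only about 15% power for 20% v 10%. The failure definition is not among the listed objectives and does not alter the length-of-stay analysis.

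**Day-7 measures.** It is tempting to say that early surgery makes the failing arm look better on opacity. The documents do not support that as a finding: they give neither the opacity expected after surgery nor how often surgery falls before day 7. A simulated reversal of direction can be produced, but only from invented values (for example a 65-point reduction after surgery against 5 without). Keeping values after later treatment is also a legitimate treatment-policy choice, in keeping with the stated intention to treat. This objection stands against making worst rank the main day-7 analysis.

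**Conclusion.** The concern holds for length of stay. As written, the comparison favours the arm with more early in-hospital deaths, and nothing shown prevents this. Under the assumptions above, the false 'shorter stay' rate rises from 2.5% to about 9–10% at 20% v 10% mortality and 24–25% at 30% v 10%. It is 4–5% at 15% v 10%, about 5% and 8% for the two larger gaps if deaths come around day 10, and unchanged when mortality is equal. The mechanism follows from the plan's own definitions; the size does not.

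For day-7 opacity and WBC/CRP, the documents support only that the handling of death and surgery is unspecified. The direction and size of any distortion cannot be derived from them.

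This is a cheap improvement to a secondary outcome that should be made before analysis. It does not touch the primary outcome.

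**What to change.** Add to section 3.7 (Statistical Analysis):
- Patients who die in hospital receive the worst rank for length of stay, and arms are compared by Mann-Whitney. Days in survivors are reported descriptively beside 30-day mortality.
- Day-7 opacity and WBC/CRP have a sensitivity analysis in which patients who died or had surgery before day 7 are ranked worst.

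Use one start point for length of stay in section 2.3 and on the data sheet.

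**Cost.** The length-of-stay rule needs one sentence and no new data, because outcome upon discharge is already recorded. The day-7 analysis needs explicit dates of death and surgery on the data sheet; it shows only yes/no entries and a grid of visit days for surgery.

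**Downside.** The result is a rank comparison that partly reflects mortality. Even with identical survivor stays it declares the higher-mortality arm worse in about 11% of trials at 20% v 10% and 32–36% at 30% v 10%. Reporting survivors' days and mortality beside it lets the reader see which of the two drives the result.

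Days alive and out of hospital to day 30 is not an available substitute: readmission is recorded only as yes/no and only for a similar complaint. It would need readmission days to be collected.

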## 2.4 Study Hypothesis

1. Subjects in the IPFT has more volume of pleural fluid drainage compared with pleural irrigation group
2. Subjects in the IPFT has greater reduction of inflammatory parameters compared with pleural irrigation group
3. Subjects in the IPFT has shorter length of hospital stay compared with pleural irrigation group
4. Subjects in the IPFT has less surgical referral rate compared pleural irrigation group
5. There is no difference of mortality rate between both groups

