#### 3.3 Sample size and Power of Study

By using power and sample size programme calculator :

Prior data indicate that the failure rate among controls is 0.15. If the true failure rate for experimental subjects is 0.32, we will need to study 39 experimental subjects and 39 control subjects to be able to reject the null hypothesis that the failure rates for experimental and control subjects are equal with

probability (power) 0.8. The Type I error probability associated with this test of this null hypothesis is 0.5. We will use a continuity-corrected chi-squared statistic or Fisher's exact test to evaluate this null hypothesis.

N = 39+/-4 (IPFT with alteplase and DNase) and 39+/-4 (pleural irrigation with normal saline)

Study used as a reference :

Pleural irrigation trial (PIT): a randomised controlled trial of pleural irrigation with normal saline versus standard care in patients with pleural infection Clare E. Hooper, Anthony J. Edey, Anthony Wallis, Amelia O. Clive, Anna Morley, Paul White, Andrew R.L. Medford, John E. Harvey, Mike Darby, Natalie Zahan-Evans and Nick A. Maskell,

Reference for sample size taken from the primary outcome of this research in which patients receiving saline irrigation had a significantly greater reduction in pleural collection volume on computed tomography compared to those receiving standard care (median (interquartile range) 32.3% (19.6–43.7%) reduction versus 15.3% (–5.5–28%) reduction) (  $p < 0.04$ ).

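### Hypothesis 5 asserts equal mortality, but the only planned analysis is a difference test with no margin or confidence interval, which can reject equality but cannot support it

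*Combined protocol and SAP*

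**What the plan says.** Section 2.4 numbers five hypotheses. The first four are directional and favour the fibrinolytic arm: more drainage, a greater fall in inflammatory markers, a shorter stay and fewer surgical referrals. The fifth is a statement of equality: "There is no difference of mortality rate between both groups". Section 2.3 lists "Mortality rate at 30 days" as the last of the secondary outcomes.

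The Statistical Analysis section (the second of two sections numbered 3.7) gives one rule for binary outcomes: "For qualitative data, Chi-Square test and Fisher's Exact test will be used". Significance is judged at 0.05, with a Bonferroni adjustment for multiple comparisons. No equivalence or non-inferiority margin appears anywhere in the document, and no confidence interval is planned for any outcome.

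Section 3.3 plans 39 ± 4 patients per arm. That figure comes from treatment failure rates of 0.15 and 0.32, with "probability (power) 0.8". Mortality plays no part in it.

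**The concern.** Chi-square and Fisher's exact tests take equality as their null hypothesis. A small p-value is evidence against equality. A large one shows only that the data did not exclude it, and in a small trial with few deaths that is weak information. For hypotheses 1 to 4 the plan's logic works, because rejecting the null supports the stated claim. For hypothesis 5 it is reversed, because the claim is the null itself and no outcome of the planned test can support it.

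What is at stake is a safety statement. Chapter 1 says the study aims to develop a treatment algorithm and to assess the efficacy and safety of the regimen. A conclusion that mortality did not differ would feed into that, and nothing in the plan prevents it from being drawn from a p-value above 0.05.

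Two features of the plan would make such a conclusion weaker still. Section 3.6 allows cross-over at any point with analysis by intention to treat, which tends to pull the arms together. Any Bonferroni adjustment makes non-significance more likely, so a step meant to be cautious would favour hypothesis 5.

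**Working it through.** **The plan's own sample size.** Section 3.3 gives p1 = 0.15, p2 = 0.32, power 0.8, a Type I error of 0.5 and a continuity-corrected test. Two-sided testing is assumed, because the null is equality. With d = 0.17 and mean rate 0.235:

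- n = [z(0.75)·√(2 × 0.235 × 0.765) + z(0.80)·√(0.15 × 0.85 + 0.32 × 0.68)]² / d²
- = [0.6745 × 0.5996 + 0.8416 × 0.5875]² / 0.0289 = 27.96
- Continuity correction: (n/4)·[1 + √(1 + 4/(n·d))]² = (27.96/4) × (2.357)² = 38.8, rounded up to 39.

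This matches the stated 39 per arm. The Type I error of 0.5 in that calculation is a separate matter. What counts here is that 39 was derived for treatment failure, so it carries no assurance about mortality.

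**Inputs for mortality.** n = 39 per arm and 1:1 allocation come from the documents. The 0.05 level comes from the Statistical Analysis section and is taken as two-sided. The mortality rates are assumptions. The only mortality figure in the documents is an upper level of 20–35% for immunocompromised patients (Chapter 1), which is not a planning rate for this trial.

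**Chance that a true doubling is non-significant.** Power is the sum of the binomial probabilities of every pair of death counts (x, y) for which the test gives p < 0.05. The miss rate is 1 − power.

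| True mortality | Power, uncorrected chi-square | Power, exact Fisher | Missed (chi-square to Fisher) |
|---|---|---|---|
| 5% v 10% | 14.2% | 4.0% | 86–96% |
| 10% v 20% | 24.1% | 15.54% | 76–84% |
| 20% v 40% | 50.3% | 39.4% | 50–61% |
| 35% v 70% | 89.3% | 84.3% | 11–16% |

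Across the planned 35 to 43 per arm, power at 10% v 20% runs from 21.9% to 26.4% (chi-square) and from 12.9% to 16.9% (Fisher).

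In counts, with 39 per arm, 2 v 8 deaths gives Fisher p = 0.087 and uncorrected chi-square p = 0.042. For 4 v 11 deaths the values are 0.083 and 0.044. Fisher first falls below 0.05 at 2 v 9 and at 4 v 12. The plan names both tests without a rule for choosing between them, so with such counts the choice alone decides whether hypothesis 5 is rejected.

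**Precision when the observed rates are equal.** Wald 95% half-width = 1.96·√(2p(1 − p)/39):

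- p = 0.05: 1.96·√(0.095/39) = 0.097
- p = 0.10: 1.96·√(0.18/39) = 0.133
- p = 0.20: 1.96·√(0.32/39) = 0.178

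The Newcombe interval is similar or slightly wider: ±12.3 points at 2 v 2 deaths, ±14.7 at 4 v 4 and ±17.9 at 8 v 8.

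**What an equality claim would need.** Take an assumed 10-point margin, equal true mortality of 10% and power 0.8. Two one-sided tests at 0.025 need 2 × 0.1 × 0.9 × (1.960 + 1.282)² / 0.10², which is 190 per arm. One-sided non-inferiority at 0.025 needs 142 per arm. At 39 per arm only wide margins are within reach, for example about 20 points at 10% mortality.

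**The case against.** The strongest reply is that hypothesis 5 may be meant only as a null hypothesis or as the investigators' expectation. On that reading a difference test is coherent, because it can reject the statement. This stands in part: chi-square and Fisher are not wrong tests for comparing mortality, and the fault lies in what they are asked to support. It does not remove the problem. The other four hypotheses are written as claims to be supported, the fifth is numbered among them, and nothing tells the reader to treat it differently.

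A reader might infer that the plan will declare equal mortality whenever p exceeds 0.05. The documents do not say so. They name tests and a threshold, and give no rule for interpreting a non-significant result. The risk is a misreading that the plan leaves open, not one that it commits to.

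A reader might also infer that the trial would very likely miss a doubling of mortality whatever the base rate. The table does not support that. It is so at 5% or 10% base mortality, about even at 20%, and no longer so at 35%. Quoting Fisher alone at a 10% base would also overstate the case, since uncorrected chi-square misses 76% there rather than 84%.

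Finally, mortality is secondary, low power for death is normal in a trial of about 78 patients, and the absence of confidence intervals is not specific to mortality. All of this is fair and limits the severity. It does not make the hypothesis supportable.

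**Conclusion.** The point holds as a mismatch between a hypothesis of equality and an analysis that cannot establish equality. That part follows from the text alone and needs no assumed rate.

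Its size depends on the unknown base mortality. At 5–10% a true doubling would go undetected in roughly three-quarters or more of trials. At 20% the chance is 50–61%, and at 35% it is 11–16%. Even identical observed rates would leave differences of about 10 to 18 points compatible with the data over base rates of 5–20%. These figures rest on assumed mortality rates, 39 per arm with complete 30-day follow-up, a two-sided 0.05 level and no Bonferroni adjustment.

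Severity is modest: it concerns a secondary outcome and what may be concluded from it, not the design or the primary analysis.

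**What to change.** Remove hypothesis 5 from section 2.4 and replace it with an estimation objective: deaths within 30 days by randomised arm, with the risk difference and an exact or Newcombe 95% confidence interval. Add the interval to the Statistical Analysis section, and state there that a non-significant test of mortality will not be interpreted as showing no difference. If a test is kept, say which of the two will be used.

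The cost is about two sentences. The data collection sheet already records 30-day mortality and its cause, so no extra patients or data are needed. The sheet counts the 30 days from first treatment while section 2.3 names no starting point, so the new wording should fix one.

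The trial gives up a claim of equal mortality, which it could not have supported. The alternative is to keep the claim with a justified margin and a matching sample size. On the illustration above that would mean roughly 140 to 190 per arm, which is out of proportion for a secondary outcome in this trial.
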